3.6 Data Collection

3.6.1 Timing of Sample Collection

Upon admission to labour and delivery, and prior to delivery wherever possible, the following maternal sample types will be collected: nasopharyngeal or oropharyngeal swab, peripheral blood, ano-rectal swab and vaginal mucosa collected through a vaginal swab. At delivery, wherenever possible, we will collect an amniotic fluid sample through direct syringe aspiration. Should the maternal biological samples not be able to be collected prior to or during delivery, samples may be collected post-delivery, prior to discharge.

Immediately following delivery, we will collect cord blood and placenta samples (including submaniotic swab). Prior to discharge from the hospital, we will collect a neonatal nasopharyngeal swab sample (approximately 12-24 hours post-birth) and a breastmilk sample (nearest to first lactation as possible). The timing of sample

collection is summarized in **Table 2** presented below. Pathologists at each participating site will be requested to send the local placenta pathology report and slides (or scanned slides if slides are not feasible), collected as per standard of care.

Table 2. Timing of biological sample collection

	Timing of sample collection				
Biological sample	Prior to delivery	At delivery	Post deliver	ТY	
Maternal peripheral blood	Х				
Maternal nasopharyngeal or oropharyngeal swab	Х				
Maternal vaginal mucosa	X (swab prior to ۱ membranes, if				
Maternal ano-rectal swab	Х				
Amniotic fluid		Х			
Cord blood		X (from blood gases)			
Placenta (includes subamniotic swab)			X (ex vivo)		
Neonatal nasopharyngeal swab			X (12-24 hours po	st-birth)	
Breastmilk sample			Х		

3.6.2 Sample Collection Process and Storage

In order to reduce sample degradation and ascertain consistency between sites, samples will be collected and stored as per the Lab Manual following requirements for working with biohazardous materials and Transportation of Dangerous Goods (TDG) while abiding by local institutional obligations. We will collect date of diagnosis for participants. Should the date of diagnosis not be available, we will use date of COVID-19 hospital admission as the estimated date of viral onset. Details of sample collection (e.g. date, time, methodology) will be documented on the Sample Collection Information Form. The Form will be used to review duration of infection where appropriate, and relationship to gestational age. **Figure 1** presents the general study workflow related to all samples variants. Detailed sample collection procedures are outlined in the Lab Manual which is provided to each participating site.

Samples collected at each participating site will be affixed with a patient label containing the patient name and medical record number [MRN]. At least one patient label will be shipped alongside samples to identify patient source of the samples. This will avoid the possibility of errors, and will also reduce the workload of the healthcare staff collecting the samples during a pandemic urgent situation. Further, the patient identifiers on these samples (patient name and MRN) will be used to link the clinical data to the BORN Ontario Birth Registry for supplemental pregnancy and demographic information upon participant consent.

[figure not shown]

Figure 1: Study Workflow

3.6.3 Shipment of Samples

All specimens will be transported as UN3373 Biological Substance Category B with appropriate packaging, labelling and documentation.

Samples will be received by the Study Coordinating Centre (SCC), the Ottawa Hospital Research Institute (OHRI). The patient identifiers will be removed and a COPE Network unique study ID will be affixed and the study ID and participant information will be retained in a master log stored on the secure network at the OHRI. The SCC andauthorized personnel at participating sites will have access to their master file through the hospital shared drive, which is stored on the SCC hospital shared drive. Once the samples are received and assigned a study ID, the samples will then be distributed to specific laboratories within Ottawa for analysis (see **Table 3** for list of laboratories within Ottawa).

[figure not shown]

Table 3. Laboratories receiving shipped samples

3.6.4 Data Linkage with the BORN Ontario Birth Registry

The Better Outcomes Registry and Network (BORN) Ontario birth registry is a province-wide database, held and administered at the Children's Hospital of Eastern Ontario (CHEO). The database captures all hospital births >500 grams or >20 weeks' gestation in the province. The routine data collection includes information on maternal demographics and health behaviours, pre-existing health problems, obstetric complications and birth outcomes. Data are collected from medical records, clinical forms, and patient interview when a woman is admitted to hospital to give birth.

In response to the urgent public health crisis, BORN Ontario recently approved the collection of data for any cases of COVID-19 infected pregnant individuals admitted to Ontario hospitals between March 1, 2020 and March 1, 2021 (or until the pandemic is declared over and 40 weeks pass to allow collection from newly pregnant individuals who will continue their pregnancy) for the registry purpose of facilitating and improving care. This

includes information from Ontario hospitals on COVID-19 laboratory results, illness, and outcomes. In order to support the analysis and minimize hospital staff burden, we will utilize the data collected as part of this BORN Ontario COVID-19 initiative to provide clinical and demographic information on our participants. Please refer to **Appendix 1** for a list of the data elements (COVID-19 Case Report Form) that will be collected through the study through the data linkage with BORN Ontario.

BORN Ontario has policies for the secure transfer and retention of personal health information in accordance with Ontario's health privacy legislation, the Personal Health Information Protection Act (PHIPA). The data and personal health information (PHI) collected by BORN is securely held, and all analyses will be performed within the BORN secure network environment. The data will be accessible only to the BORN Ontario Analyst who links and assembles the files, and to the study staff at the OHRI who will be responsible for conducting the analyses.

COVID-19 data collection in BORN Ontario is currently optional for hospitals in the province. To ensure data completeness, some sites may complete the Case Report Form which will capture the same data that is collected in BORN Ontario and additional laboratory or clinical variables from routine clinical tests performed for COVID-19 suspected or positive patients Data in the CRF will be sent to the SCC securely and confidentially using a restricted-access database in SharePoint.

Data from medical charts and sample analysis will be sent to BORN Ontario for linkage with the BORN Ontario data, including both the COVID-19 data and routinely collected perinatal and infant health data, upon participant consent.

3.9 COPE Network Site-Specific Placental Control Group

Evidence has shown that placentas not complicated by SARS-CoV-2 may also display pathological changes, thus highlighting the importance of including a sufficient number and variety of controls that would allow valid comparisons to be made. Subgroup analyses based on mode of delivery (cesarean section vs. vaginal) as well as maternal comorbidities (including but not limited to: preeclampsia, chronic hypertension, gestational and chronic diabetes, IUGR) will necessitate having sufficient controls with these characteristics.

In addition to the control participants recruited at TOH, COPE Network Sites with capacity to collaborate will be asked to send slides and pathology reports of placentas that, to the best of their knowledge, were not complicated by SARS-CoV-2. The following clinical indications may warrant placental pathology examination and would provide valuable control comparisons:

- Multiple births (both dichorionic and monochorionic)
- Preterm birth (<34 weeks of gestation)
- Placenta previa
- Elective Cesarean section delivery
- Clinical suspicion of abruption

• Compromised clinical condition of neonate (intensive care admission, cord pH<7.0, Apgar score of less than 5 at 5 minutes, ventilatory assistance, hematocrit less than 25%, hydrops fetalis, congenital anomalies)

- Fetal congenital anomalies
- Maternal cancer history

Placentas that were sent for pathology examination for reasons listed above, between April 2020 to July 2021 may be included in the 'pandemic' control group, and placentas sent to pathology prior to March 2019 (i.e., a year prior to the beginning of the pandemic) will be included in the 'pre-pandemic' control group for the purpose of comparing COVID-19 placental pathology to background pathology during both time points.

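### Section 3.9 sets eligibility for network control placentas but no rule for which eligible ones a site sends, so selection could take place with the lesion findings already known

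*Combined protocol and SAP*

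**What the plan says.** Section 3.9 of the combined protocol and SAP adds site-supplied placentas to a separate set of controls from TOH. The request reads: "COPE Network Sites with capacity to collaborate will be asked to send slides and pathology reports of placentas". Absence of infection rests on what each site happens to know ("to the best of their knowledge, were not complicated by SARS-CoV-2"). The material is defined by two things:

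- **Indication.** "The following clinical indications may warrant placental pathology examination and would provide valuable control comparisons"; a list follows, covering among others multiple births, early preterm birth, elective cesarean and compromised neonatal condition.
- **Date.** Placentas sent to pathology "between April 2020 to July 2021 may be included in the 'pandemic' control group". The pre-pandemic group is "placentas sent to pathology prior to March 2019", with no start date.

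Inclusion is permissive for the pandemic group only; the pre-pandemic group is included outright. The section stresses "the importance of including a sufficient number and variety of controls that would allow valid comparisons to be made" and gives the controls' role as "for the purpose of comparing COVID-19 placental pathology to background pathology during both time points". It also wants controls for subgroup analyses by mode of delivery and maternal comorbidity.

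The section gives no target number of controls, no quota by site or indication, and no consecutive or random selection. It does not say that the person choosing should not see the report. Section 4.2 describes no analysis of the comparison between COVID-19 and control placentas.

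**The concern.** In this comparison the lesion is the outcome, and the report that lists the lesions travels with the slides. An archive with no start date is unlikely to be sent whole, so somebody has to pick. If the pick depends at all on what the report says, the controls stop showing background prevalence. A site might favour clean examples as controls, or memorable abnormal ones.

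This is a separate matter from which hospitals or indications contribute. It would operate within one hospital and one indication. Adjustment for site, indication or gestational age therefore leaves it in place, because inside each stratum the controls are still selected on the outcome. Blinded central re-reading corrects how a slide is read, not which slides arrived.

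Placental pathology is the fourth outcome in section 3.5 and part of the third, so a reported outcome of the study is exposed.

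**Working it through.** **Figure in the plan.** There is none to reproduce. Section 4.1 states that a power calculation could not be done and gives only an anticipated 150 to upwards of 200 participants. No lesion rate, control number, test or significance level is given for this comparison.

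**Step 1: is the outcome on file when a placenta is sent?** For the pre-pandemic group, yes: these are archived placentas from before March 2019. For the pandemic group it is strongly implied, because they too had been sent to pathology and the report is part of what is requested.

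**Step 2: is the case side the same?** Section 3.6.1 requests the local report and slides for the participants, who form an enumerated group. Complete sending is not guaranteed, but there is a list to check against. Section 3.9 describes no such list for controls.

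**Step 3: bias formula.** Let p be the true lesion prevalence among eligible controls, and r the chance that a placenta with the lesion is sent relative to one without it. Let w be the share of controls from network sites, the rest being unselected TOH controls.

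- Prevalence among network controls as sent: p·r / (p·r + 1 − p)
- Prevalence among all controls: q = w·[p·r / (p·r + 1 − p)] + (1 − w)·p
- Apparent odds ratio with no true effect: [p/(1 − p)] / [q/(1 − q)], which equals 1/r when w = 1

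**Step 4: numbers.** All of the following are assumptions: p = 0.30, no true effect, equal groups of 150 or 200 (section 4.1's range for participants, borrowed for controls too), and a two-sided 5% pooled test of two proportions.

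For r = 0.5 and w = 1: q = 0.15/(0.15 + 0.70) = 0.176, and the odds ratio is 0.4286/0.2143 = 2.0. For r = 0.5 and w = 0.5: q = (0.176 + 0.300)/2 = 0.238, and the odds ratio is 0.4286/0.3127 = 1.37.

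The false-positive rate is Φ[(d − 1.96·s0)/s1] + Φ[(−d − 1.96·s0)/s1]. Here d = |p − q|, s0 is the pooled standard error and s1 the unpooled one. For r = 0.5, w = 1 and 150 per group, d = 0.1235, s0 = 0.0492 and s1 = 0.0487, which gives 71%.

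| r | Network share w | Control prevalence | Apparent OR | False positives, 150 / 200 per group |
|---|---|---|---|---|
| 0.5 | all | 17.6% | 2.00 | 71% / 83% |
| 0.5 | half | 23.8% | 1.37 | 23% / 29% |
| 0.8 | all | 25.5% | 1.25 | 14% / 17% |
| 0.8 | half | 27.8% | 1.11 | 7% / 8% |
| 1.5 | all | 39.1% | 0.67 | 38% / 48% |
| 1.5 | half | 34.6% | 0.81 | 13% / 16% |
| 2 | all | 46.2% | 0.50 | 82% / 92% |
| 2 | half | 38.1% | 0.70 | 31% / 40% |

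**Step 5: sensitivity to prevalence.** With w = 1 the apparent odds ratio stays at 1/r whatever p is. At r = 0.5, the false-positive rates are 57% / 69% for p = 0.2 and 84% / 93% for p = 0.5.

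**Step 6: after the fix.** A consecutive or random draw made without the report sets r = 1. Then q = p, the odds ratio is unbiased and the 5% level holds, as far as this mechanism is concerned.

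**The case against.** The strongest reply is that section 3.9 nowhere says that sites choose by lesion or open reports before sending. Eligibility rests on indication, date and absence of known infection, none of which is a lesion finding. That stands: the text shows an opening for outcome-dependent selection, not its occurrence. A reader might infer that sites do choose on the report and that the comparison is therefore biased. The documents do not support this, and they give no direction.

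Other points that stand:

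- The permissive wording covers only the pandemic group, and may simply mean eligible, so it does not by itself show site discretion. The gap is the missing rule, which affects both groups.
- Background comparison is not the controls' only purpose; section 3.9 also names subgroup analyses.
- The groups are defined by infection, with the lesion as outcome, so this is not a case-control comparison. The bias formula is unaffected.
- The largest percentages need every control to come from network sites. TOH controls would dilute the effect, and their share is not stated.
- In the text available, numbering passes from 3.6.4 to 3.9 and there is no section 5. The Lab Manual is not included either. A sampling rule could sit in any of these, though section 3.9 refers to none.
- The stated objective in section 2 is transmission; the control comparison is supporting work.

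What does not stand is that this is merely missing detail. Selection on the outcome cannot be repaired in the analysis, and the alternative is concrete and cheap.

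**Conclusion.** The point holds as a gap in the sampling of network controls. Section 3.9 fixes which placentas qualify but not which are sent, and selection could take place with the lesion findings known. Nothing in the text available prevents or records a preference.

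The size is conditional on r, which the documents do not give. Under the stated assumptions, a strong preference (r = 0.5) produces 71–83% false positives with network controls alone and 23–29% with half unselected TOH controls. A mild one (r = 0.8) produces 14–17% and 7–8%. With no preference there is no bias from this source. These figures show what is at risk; they do not estimate what happened. The change is worth making because it costs little and later analysis cannot substitute for it.

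**What to change.** For both control groups:

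1. State a closed date window. The pre-pandemic group needs a start date; without one there is no defined list to sample from.
2. Have each contributing site list all eligible placentas in the window by accession number, and draw a consecutive or random sample within indication, without sight of the report.
3. Send and include every placenta drawn, and log the numbers eligible, drawn and sent for each site and indication.

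The pandemic window closed in July 2021 and the protocol version is dated November 2024, so controls may already be in hand. For those, record how each was picked, and repeat the comparison using only sites that sent consecutive or random placentas. If a sampling rule already exists elsewhere, cite it in section 3.9.

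Cost: protocol wording and one list pull from each site's pathology system. Sites lose some discretion, and some convenience controls drop out of the sensitivity comparison, which lowers its precision.

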4. STATISTICAL METHODS

4.1 Sample Size

Due to the novel nature of this study, the anticipated sample size it not yet known and therefore a typical power calculation cannot be performed. As of March 2nd 2021, Ontario has a total of 303, 763 confirmed COVID-19 cases reported.⁵⁰ Considering a total of approximately 13 major Ontario hospital sites will be involved in this study, our sample is anticipated to range anywhere from 150 to upwards of 200 participants.

4.2 Analysis Plan

4.2.1 Droplet Digital PCR

We will follow manufacturer instructions of the Bio-Rad QX200 Droplet Digital PCR System. We will employ a multiplex strategy that will co-amplify the viral RNA coding for the N gene in the FAM channel using US CDC primers and probe (N1) and Hong Kong primers and probe (N).^{46,47} The Hex channel will contain primers and probe for the viral RNA coding for the E gene (E-Sarbeco) designed by the WHO⁴⁸ and an internal RT and amplication control, RNAse P. This custom multiplex primer probe approach will promote high sensitivity in FAM with confirmatory specificity in Hex.⁴⁹ In brief, the 20 uL reaction mixture comprises 5 uL of Supermix, 2 uL of reverse transcriptase, 1 uL of 300 mM DTT from One-Step RT-ddPCR Advanced Kit for Probes (Bio-Rad), 1 uL of mixture of primers and probe and 11 uL of RNA template. Each reaction mix was converted to droplets using the QX200 Droplet Generator (Bio-Rad,), transferred to a 96-well plate (Bio-Rad), heat sealed and amplified in a GeneAmp System 9700 thermal cycler (Applied Biosystems). The thermal cycling conditions were as follows: 45 for 10 min (reverse transcription); 95 for 5 min; and 40 cycles of 95 for 15 sec, and 58 for 30 sec. The cycled plate was then transferred to the QX200 Droplet Reader (Bio-Rad) and analyzed using the QuantaSoft droplet reader software (Bio-Rad). Reactions containing more than 10,000 droplets were treated as effective and involved in data analysis.

DdPCR data analysis will be performed using Quanta Soft analysis software v 1.7.4.0917 (Bio-Rad) which was included with the droplet reader and will be used to calculate the concentration of the target DNA sequences,

along with their Poisson-based 95 % confidence intervals. The positive populations for each primer/probe are identified using positive and negative controls with single (i.e., not multiplexed) primer–probe sets. The concentration reported by QuantaSoft equals copies of template per microliter of the final 1× ddPCR reaction, which will also used in all the results. In addition, plots of linear regression will be conducted with GraphPad Prism 7.00, and probit analysis for lower limit of detection (LLoD) will be conducted with StatsDirect software v3.2.9. Lower limit of quantitation (LLoQ) and LLoD are defined as the lowest concentration at which 95 % and 50 % of positive samples are detected, respectively.

[figure not shown]
We will summarize the nucleic acid test results of all clinical samples collected (vaginal mucosa, amniotic fluid, cord blood, placenta, maternal nasopharyngeal/oropharyngeal and neonatal nasopharyngeal swab, breastmilk) to ascertain the possibility of intrauterine vertical transmission and post-partum feeding transmission. A positive test result reflects the presence of coronavirus in these clinical samples and will be indicative of possible mother-to-infant transmission. Laboratory test results however will be considered within the context of clinical observations and epidemiological data when making the final diagnosis decisions. In addition, binary logistic regression will be conducted to further investigate the association between coronavirus in placenta and the presence of fetal/neonatal complications.

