3. METHODOLOGY

3.1 Study Design

In order to assess the mother-to-infant and potential vertical transmission of SARS-CoV-2 infection in pregnant women, maternal and neonatal biological samples will be prospectively collected from women with confirmed or suspected COVID-19 at participating hospitals across Ontario. Samples will be tested for the coronavirus serology and viral load.

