3.5 Study Outcomes

Outcomes for the study objective will be ascertained through the collection and testing of biological samples from the mother and/or infant. Specifically we will:

- 1) Assess maternal nasopharyngeal or oropharyngeal swab, vaginal mucosa, ano-rectal swab, amniotic fluid, placenta (including subamniotic swab), breastmilk, cord blood and neonatal nasopharyngeal swab for RNA particles of coronavirus, by ddPCR.
- 2) Assess maternal serum for anti-coronavirus antibodies, by immunoassay.
- 3) Examine the impact of coronavirus on the neonate with respect to serology and viral load, in addition to placenta pathology findings and ddPCR.
- 4) Assess vertical transmission and the effect of coronavirus through placental pathology examination using placental pathology synoptic report (**Appendix 2**).

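### Viral load is to be reported per microlitre of ddPCR reaction with no conversion to the specimen, so equal reported loads or detection limits can mean different specimen loads wherever extraction volumes differ

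*Combined protocol and SAP*

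**What the plan says.** Section 4.2.1 sets the unit of the ddPCR output: "The concentration reported by QuantaSoft equals copies of template per microliter of the final" 1× reaction, "which will also used in all the results". It also gives the reaction recipe: "the 20 uL reaction mixture comprises 5 uL of Supermix, 2 uL of reverse transcriptase, 1 uL of 300 mM DTT", followed by "1 uL of mixture of primers and probe and 11 uL of RNA template".

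Section 3.1 makes load a study measurement: "Samples will be tested for the coronavirus serology and viral load". Section 3.5, item 3, makes it part of an outcome: "Examine the impact of coronavirus on the neonate with respect to serology and viral load". Item 1 of 3.5 lists what goes through ddPCR: maternal respiratory, vaginal and ano-rectal samples, and then "amniotic fluid, placenta (including subamniotic swab), breastmilk, cord blood and neonatal nasopharyngeal swab for RNA particles of coronavirus, by ddPCR". Maternal serum is listed for antibodies only, so the blood specimen at issue is cord blood.

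On targets, 4.2.1 plans to "co-amplify the viral RNA coding for the N gene in the FAM channel" using two N assays. It puts the E gene in the Hex channel together with RNAse P, which is described as an internal control and not as a normaliser. It also says that the positive populations are identified separately for each primer/probe set.

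The closing paragraph of 4.2.1 gives the planned use of the results: a summary across specimen types, with a positive result read as possible mother-to-infant transmission, and a binary logistic regression on coronavirus in placenta.

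**The concern.** Copies per microlitre of reaction is a property of the PCR well. It depends on how much virus was in the specimen, and also on how much specimen was extracted and into what volume the RNA was eluted. The specimens here are physically unlike: fluids, tissue and swab eluates. If extraction volumes differ between them, or between sites or batches of one type, two specimens with the same load give different reported values, and two with the same reported value carry different loads.

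Two things are at stake. The first is the viral-load measurement itself, which could not be read as a quantity in the specimen or set against results from other studies. The second is the meaning of a negative. Section 4.2.1 defines LLoD and LLoQ as concentrations. If they stay in reaction units, a negative in milk and a negative in amniotic fluid may exclude different amounts of virus, yet both feed the judgement about intrauterine and feeding transmission.

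**Working it through.** **Inputs from 4.2.1.** Supermix 5 µL, reverse transcriptase 2 µL, DTT 1 µL, primer/probe mix 1 µL, RNA template 11 µL; stated total 20 µL.

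**Step 1: reproduce the stated reaction volume.** 5 + 2 + 1 + 1 + 11 = 20 µL. It agrees.

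**Step 2: well to extract.** For a reported value C in copies/µL of reaction, copies per well = 20 × C and copies/µL of extract = C × 20/11. With C = 1: 20 copies per well, and 20/11 = 1.82 copies/µL of extract. This factor is the same for every reaction, so it rescales all values and distorts no contrast.

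**Step 3: extract to specimen.** Specimen load = C × (20/11) × elution volume / specimen input. The documents give neither volume for any specimen type, so this step cannot be done from them. The volumes below are assumptions, used only to show the range for C = 1.

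| Assumed input | Assumed eluate | Specimen load when C = 1 |
|---|---|---|
| 1 mL fluid | 50 µL | 1.818 × 50 / 1 = 91 copies/mL |
| 0.5 mL fluid | 50 µL | 1.818 × 50 / 0.5 = 182 copies/mL |
| 0.2 mL fluid | 50 µL | 1.818 × 50 / 0.2 = 455 copies/mL |
| 0.2 mL fluid | 100 µL | 1.818 × 100 / 0.2 = 909 copies/mL |
| 0.1 mL fluid | 100 µL | 1.818 × 100 / 0.1 = 1,818 copies/mL |
| 30 mg tissue | 50 µL | 1.818 × 50 / 30 = 3.03 copies/mg |
| 10 mg tissue | 100 µL | 1.818 × 100 / 10 = 18.18 copies/mg |

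With the same 50 µL eluate, inputs of 0.2 mL and 1 mL give 455/91 = 5-fold. Across all the fluid rows the range is 1,818/91 = 20-fold. With equal input and eluate the ratio is 1.

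**Step 4: detection limit.** The same formula applies with C set to the limit. A limit of 1 copy/µL of reaction (illustrative) would be 91 copies/mL in one fluid and 455 copies/mL in another under the volumes that give the 5-fold ratio.

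**Step 5: what does not change.** A positive or negative call is made on droplets in the well, and relabelling the unit does not move it. The logistic regression uses coronavirus in placenta and is likewise untouched.

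**The case against.** The strongest reply is that no stated analysis depends on the unit. The closing paragraph of 4.2.1 plans a summary of test results and a regression on placental virus. Nowhere is a comparison of load between milk, swab, fluid and tissue specified. The load outcome in 3.5 concerns the neonate, whose own direct specimen is the nasopharyngeal swab; a comparison with the maternal swab is between like specimens, apart from the oropharyngeal alternative, and nothing shows that the two are extracted differently. Extraction volumes may be fixed or recorded in laboratory documents that are not available here (3.6.2 refers to a Lab Manual for collection and storage), in which case the loss is recoverable. Reaction units are also natural in an assay description.

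Most of this stands, and it limits the point to the load measurement and the detection limit. It does not remove it. The rule is written for all results, load is a named measurement and part of an outcome, and no conversion is given.

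A reader might go further and infer that loads cannot be compared at all, or that the planned analysis is distorted 5-fold. The documents support neither: the volumes are unknown, the 5-fold figure rests wholly on assumed inputs, and no cross-specimen load contrast is planned. A reader might also infer that load will be taken as a FAM total, counting one genome once or twice because two N assays share that channel. The plan does not say so, and its identification of positive populations per primer/probe set points the other way. What remains is that it does not name the target from which load is taken.

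**Conclusion.** The point holds as a reporting rule that should be changed. As written, every ddPCR result is a well concentration, and the documents carry it only as far as the extract (constant factor 1.82). Reported loads, and any LLoD or LLoQ in this unit, can stand for different specimen loads wherever input or elution volumes differ. The size cannot be established: it is nil among fluids if volumes are equal, and 5-fold under the assumed 0.2 mL versus 1 mL inputs with a common eluate. Positivity calls and the planned regression are not affected. The conclusion assumes that no unseen document already overrides the unit rule with a per-specimen conversion.

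**What to change.** Keep reaction units for assay validation, and replace the rule that extends them to all results with the following.

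- Report viral load and the detection limit per specimen unit: copies/mL for fluids and cord blood, copies/mg for placenta, copies/swab for swabs. Compute each as reaction copies/µL × (20/11) × elution volume / specimen input; for swabs, the input is the fraction of the swab eluate extracted.
- Tabulate input and elution volumes by specimen type.
- Compare loads only within like specimens. Per mL, per mg and per swab share no denominator, so conversion alone does not make the types comparable. Across types, compare positivity, read alongside each type's detection limit.
- Base load on one named target resolved by droplet amplitude: a single N assay in FAM, or E separated from RNAse P in Hex. E shares its channel too, so choosing it does not avoid the need for separation.

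The cost is a few sentences, one table and a spreadsheet conversion, with no new samples or assays where volumes were recorded. The downside is that samples without recorded volumes remain qualitative only.
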